10.2 Clinical Data Management

Clinical Data Management (CDM) *Clinical data management*), enables the generation of high-quality, reliable and statistically valuable data. CDM is the process of collecting, cleaning, and managing the information of the subjects of a study in accordance with regulatory standards (guidelines 21 CFR Part 11, ICH and GCP). It covers eCFR design, comments on the eCFR, database design, capture (*Data entry*), validation (*source document verification, SDV*), discrepancy management (*You want*), medical coding (*Medical Coding*), extraction (*Soft lock*) and database shutdown (*Hard Lock*). [57]

In accordance with roles and responsibilities, multiple users can be created, whose types of access to the eCRF can be limited to capture (principal investigator, IP), medical coding, database design, or quality control (*Quality Check*). The handling of discrepancies will be carried out based on the flow in Figure 5.[57, 58]

The following roles will be included in the CDM team:

- Data Manager,
- Database designer/programmer,
- Medical coder,
- Clinical Data Coordinator,
- Quality control, and
- Capturist (*data entry associate*). [57]

[figure not shown]

Figure 4. Management of discrepancies (MN, medical note; CRA, clinical monitor; SEC *self-evident correction*)

10.3 Statistical methodology

The statistical analysis plan was developed considering the evaluation criteria described in the study protocol.

The statistical analysis will be carried out by personnel of Laboratorios Sophia, S.A. de C.V. The SPSS statistical package version 19.0 for Windows (IBM Corporation, Armonk, NY, USA) will be used. The coding will be done using consecutive numbers. The data will be collected and sorted in an Excel spreadsheet (Microsoft® Office). The data will then be exported to the SPSS package platform. The variables will be categorized according to their nature (see Board 4 Triangulation of concepts)

The statistical tests used will be following the corresponding assumptions for non-parametric statistics.

10.3.1 Population Analysis

The statistical analysis will be presented to give a general summary of the subjects entered the study and a view of the safety and tolerability of its results. The data provided by the research site will be summarized for this purpose, according to its nature. The Shapiro-Wilk test will be performed to find out if the quantitative data are distributed in a normal way ($p>0.05$).

The results of the quantitative variables will be presented in measures of central tendency: mean, standard deviation, maximum and minimum. Changes in pupillary diameter, near visual acuity, BCVA and OCI will be expressed as continuous variables. Changes in IOP, HR, systemic blood pressure, and TF will be expressed as discrete variables.

The result of the nominal and ordinal qualitative variables will be presented in frequencies, proportions and/or percentages. For these, 2 x 2 frequency tables will be built. All percentages will be presented with decimal.

The level of difference to consider significance will be an alpha (α) of 0.05 or less. The triangulation between the variable type and the measurements is shown in the Board 4 Triangulation of concepts.

Board 4 Triangulation of concepts

Variable Type	Variable	A1	A2	B1	C1	C2	D1	D2	D3	E1	E2	E3	E4	E5
Selection														
A1	Demographic			D										
A2	Medical History/Selection Criteria				D									
Basal														
B1	Comprehensive ophthalmological evaluation			DT	D	TB			TB					
Safety & Tolerability														
C1	Incidence of AE*				TB			TB						
C2	Incidence of photophobia				TB	TB		TB			T			
Secondary Security Outcome														
D1	Pupillary diameter					B	TB							
D2	Incidence of AD				TB	TB		TB						
D3	Near visual acuity			D			TB	B						
Exploratory														
E1	BCAV			D			TB		B					
E2	PIO			D			TB		B					
E3	Corneal and conjunctival stains with fluorescein and lysmine green			D			TB			B				
E4	Vitals signs			D			TB			B				
E5	OCI			D							B			

Abbreviations: BCVA, best corrected visual acuity; B, bivariate analysis; D, descriptive statistics; AE, adverse event; OCI, ocular comfort index; M, multivariate analysis; IOP, intraocular pressure; T, 2x2 contingency table. *Unexpected-related AEs.

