measures of central tendency: mean, standard deviation, and ranges. Qualitative data will be presented as frequencies and percentages. The statistical analysis to rule out differences will be carried out by means of non-parametric statistics. The Kolmogorov-Smirnov statistic will be used for a sample and the Mann-Whitney statistic (when applicable). The analysis for qualitative variables will be performed by means of Pearson's χ^2 (Chi-square) test or Fisher's Exact test (when applicable). For all analyses, a $p < 0.05$ and an alpha of 0.05 (two-tailed) will be considered significant.

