7.4.4 Definition of variables, methods and scales for their measurement

Board 1. Operational definition of variables

Variable	Conceptual Definition	Operational Definition	Measurement Type	Reference value	Statistical test
Incidence of unexpected-IP-related AEs	Any adverse medical event that occurs in the clinical research subject to whom the PI was administered that has a certain causal relationship with the PI and is not expected. [36]	All AEs (according to the protocol) in which the PI suspects a causal relationship with the PI will be reported.	
 • Discrete quantitative • Nominal qualitative 	< 10%	
 • U for Mann Whitney • Pearson X² or Fisher Exact*
Photophobia incidence	Expected-PI-related AE	Present / Absent	
 • Discrete quantitative • Nominal qualitative 	< 15%	
 • U for Mann Whitney • Pearson X² or Fisher Exact*
Pupillary diameter	The natural pupil of the human eye is usually approximately circular, for a given subject, the pattern of aberrations, diffraction, depth of field and retinal illumination depends on the pupillary diameter, which in turn	The pupillary diameter results from the balance between the pupil sphincter muscle and the radial fibers of the iris that have only autonomic innervation. [37] It will be evaluated through the OPD scan.	Continuous quantitative	2 – 6 mm	Kolmogorov-Smirnov or Mann Whitney U*

Variable	Conceptual Definition	Operational Definition	Measurement Type	Reference value	Statistical test
	varies depending on the ambient lighting.				
Incidence of AD	Any adverse medical event that occurs in the clinical research subject to whom the PI was administered. [36]	All AEs (according to the protocol) will be reported and not just those where the PI suspects a causal relationship with the PI	• Discrete quantitative • Nominal qualitative	• Incidence • Seriousness (severity) • Causality	• U for Mann Whitney • Pearson X ² or Fisher Exact*
Changes in the AVMC	Clinical assessment of near visual acuity allows visual ability to distinguish letters to be assessed.	It will be evaluated by means of the ETDRS booklet for near vision (annex16.1 ETDRS Primer for Near Vision), using the font size in logMAR.	Continuous quantitative	0.1 or better	Kolmogorov-Smirnov or Mann Whitney U*

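### Board 4 crosses photophobia with an adverse-event variable that already contains it, so any association in that table is partly built in and cannot be interpreted

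*Combined protocol and SAP*

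**What the plan says.** Section 10.3.1 states that nominal and ordinal results will be given as frequencies and percentages, and adds: "For these, 2 x 2 frequency tables will be built". Board 4 in the same section then sets out which variables are crossed. Its legend gives "T, 2x2 contingency table" and "B, bivariate analysis". The row labelled "Incidence of photophobia" (C2) carries TB under column D2, and row D2 carries TB under column C2. D2 is labelled incidence of AD, read here as incidence of adverse events.

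Board 1 (Section 7.4.4) defines photophobia as an "Expected-PI-related AE", where PI stands for the investigational product. Section 7.4.5.9 lists it first among the events that can occur with PRO-201. Section 7.4.5.4 collects it through the adverse-event interrogation.

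D2 has two definitions. Board 1 says "All AEs (according to the protocol) will be reported and not just those where the PI suspects a causal relationship with the PI". Section 7.4.2 and the Synopsis make the secondary outcome the incidence of expected product-related events.

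On testing, the Synopsis says "The analysis for qualitative variables will be performed by means of Pearson's χ^2 (Chi-square) test or Fisher's Exact test (when applicable"), and Board 1 repeats those tests for both variables, alongside Mann-Whitney. The significance level is 0.05, two-tailed.

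**The concern.** Pearson's and Fisher's tests take as their null that the two classifications are independent. Here one is a subset of the other: every subject with photophobia has, by that fact, a D2 event. The table then partly measures that a part lies inside its whole. A small p-value could be taken to mean that subjects with photophobia are prone to adverse events in general, even if photophobia were unrelated to every other event. The useful question, whether photophobia goes with other adverse events, is not answered by this table. C2 is a primary variable, so a p-value attached to it is likely to be noticed.

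**Working it through.** **Table size.** Section 10.1.2 takes 24 subjects and adds 20% for losses: 24 × 1.2 = 28.8, rounded up to 29. This reproduces the plan's figure. The documents give no figure for the C2 by D2 analysis itself.

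**Why independence fails.** Since C2 lies inside D2, P(C2 and D2) = P(C2). Independence needs P(C2) = P(C2) × P(D2), that is P(C2) × [1 − P(D2)] = 0. This holds only if nobody has photophobia or everybody has a D2 event. Both definitions of D2 contain product-related photophobia, and no section removes it.

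**When the table reaches p<0.05.** Let r subjects have photophobia and k have any D2 event, out of 29. The observed table is the most extreme in its direction, with probability C(k,r)/C(29,r). For the values below the opposite tail adds nothing, so this is the two-sided Fisher p-value.
- r=1: p = k/29, giving 0.034 at k=1 and 0.069 at k=2. It is significant only if that subject is the only one with a D2 event.
- r=2: 15/406 = 0.037 at k=6; 21/406 = 0.052 at k=7.
- r=3: significant up to k=11.
- r=4: significant up to k=14. For example, k=9 (other events in 5 of the remaining 25 subjects) gives 126/23,751 = 0.005.

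**How often that happens.** Inputs from the documents: 2% photophobia (the review cited in Section 10.1.1), the 15% tolerability limit (Section 10.1.2), and 9% as a rate of adverse events (Section 10.1.1, where it is not restricted to events other than photophobia). Assumptions: 5% and 10% photophobia as intermediate values; events other than photophobia in 9%, 30% or 50% of subjects; and photophobia independent of them. Method: r follows Bin(29, p); all r are D2-positive; x of the other 29 − r follow Bin(29 − r, q); two-sided Fisher is applied to [r, 0; x, 29 − r − x], enumerated exactly.

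| Photophobia | No case at all | Rejects, others 9% | Rejects, others 30% | Rejects, others 50% |
|---|---|---|---|---|
| 2% | 55.7% | 12.9% | 1.9% | 0.1% |
| 5% | 22.6% | 43.1% | 14.1% | 1.9% |
| 10% | 4.7% | 79.1% | 47.0% | 12.0% |
| 15% | 0.9% | 93.8% | 74.1% | 28.4% |

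The second column is (1 − p)^29, for example 0.98^29 = 0.557. With no case there is nothing to test.

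At n=24 the rejection rates are 10.8%, 1.2% and 0.1% for 2% photophobia, and 88.1%, 56.4% and 14.9% for 15%.

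Uncorrected Pearson rejects more often (43.2% at n=29, 2% photophobia, 9% others). However, with four or fewer photophobia cases both expected counts in that row are below 5. Section 10.3.2.1 switches to Fisher in that situation, though it names only conjunctival hyperemia.

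**After the change.** With photophobia removed from the adverse-event side, the same scenarios at n=29 reject between 0.02% and 1.9% of the time.

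**The case against.** The strongest objection concerns what Board 4 means. As extracted it is not symmetric: row C2 has TB under C1, but row C1 has nothing under C2. Several entries look displaced, such as the demographic row's mark under B1. TB also sits on the diagonal, including pupillary diameter against itself, where a 2x2 table makes no sense for a continuous variable. It is therefore not certain that every TB is a test of row against column. Nor does any section name the test for this cell: Board 1 and the Synopsis say only when applicable, and Section 10.3.2.1 assigns Pearson or Fisher only to conjunctival hyperemia. These points stand as caveats. They do not remove the C2 and D2 entries, which agree in both rows, and the structural zero would distort any association test on this table.

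A reader might infer that a significant result is guaranteed. The documents do not support that. At their only cited photophobia rate, 2%, the chance is at most about 13% in these scenarios, and more likely than not there is no case. The 94% figure combines photophobia at the tolerability limit with 9% other events, so 1 − 0.85 × 0.91 = 23% of subjects would have some event.

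A reader might also extend the fault to unexpected related events against D2 (C1 by D2). That holds only if D2 is all events. If D2 is expected product-related events, the two sets of events are disjoint and there is no containment.

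**Conclusion.** The point holds with limits. On either definition of D2, the planned C2 by D2 table has a cell that is empty by definition, so its association is partly built in and uninterpretable. Whether it reaches p<0.05 depends on the counts: unlikely at 2% photophobia, and more likely as photophobia approaches 15% and other events are few. These sizes assume Fisher at n=29, independence of photophobia from other events, and other events at 9% to 50%.

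It might be inferred, because C2 is primary, that the primary conclusion is at risk. It is not: Sections 3.2 and 10.1.2 judge safety and tolerability by incidence against 10% and 15%, and no stated decision uses this table. The consequence is a potentially misleading secondary safety p-value.

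**What to change.** In Board 4, replace TB with D for C2 by D2, so that counts are reported without a p-value. Alternatively, define the adverse-event side as at least one adverse event other than photophobia. The descriptive option is better, because the corrected Fisher test is very conservative at this size (at most about 2% rejection under independence) and would have little chance of showing anything. Keep photophobia in D2 for the incidence table.

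State which definition of D2 applies. If it stays as all adverse events, treat C1 by D2 in the same way; if it is expected product-related events, C1 by D2 needs no change on this ground. Say also in the legend what TB means on the diagonal.

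The cost is a wording change to Board 4 and, for the second option only, one derived variable. No new data, visits or subjects are needed.

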10.3.2 Safety and tolerability analysis

10.3.2.1 Analysis for Primary Variables

An analysis of safety and tolerability outcomes will be carried out in the safety population, defined as any subject who has received at least one dose of the investigational product (PRO-201) regardless of adherence to it or adherence to the protocol (intention-to-treat population, ITT).

The statistical analysis for the primary variables of a quantitative type will be estimated by means of the Kolmogorov-Smirnov statistic for the difference in measurements, once the values have been adjusted with respect to their baseline within everyone. In cases where applicable, the nonparametric Mann-Whitney U test will be used.

For conjunctival hyperemia, Pearson's X² or Fisher's exact test will be used at expected values less than 5.

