
Elimination criteria:
 
 – Withdrawal of the letter from the FCI. – Presentation of a serious adverse event related or not to the investigational product, which at the discretion of the PI and/or sponsor could affect the patient's ability to continue with the study procedures safely. – Non-tolerability or hypersensitivity to any of the compounds used during the tests (fluorescein, lysmine green, tetracaine). – No tolerability or hypersensitivity to the investigational drug. – Adherence < 90% determined by the subject's diary 	

Research Product (PI):
 
 - PRO-201 . Atropine Sulfate 0.01%. Zapopan, Jalisco, Mexico. Ophthalmic solution Laboratorios Sophia, S.A. de C.V - Dosage: 1 drop once a day (QD) in the evening, in both eyes (AO). - Route of administration: Ophthalmic 	

Duration of treatment: 14 days
	
Duration of the subject in the study: 21 days

Evaluation criteria:
 
Primary outcome variables
 
 – Incidence of unexpected PI-related AEs (Time of Assessment [TE]: days 7, 16 and 21) – Incidence of IP-related photophobia. (TE: 7th, 16th and 21st) 
Secondary outcome variables:
 
 – Changes in pupillary diameter (ET: day 7 and 16). – Incidence of expected PI-related AEs (TE: days 7, 16, and 21). – Changes in visual acuity (TE: day 7 and 16). 
Exploratory variables:
 
 – Changes in the AVMC (TE: day 7 and 16). – Intraocular pressure (IOP) changes (ET: day 7 and 16). – Changes in corneal and conjunctival staining with fluorescein and lysmine green (ET: day 7 and 16). – Changes in vital signs (heart rate and blood pressure) (ET: day 7 and 16). – Changes in the OCI (TE: day 16). 	

Statistical methodology
 
The analysis of the data collected in the study will be carried out using the SPSS version 19.0 statistical package. For continuous and discrete quantitative variables, data will be expressed by
	

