7.3 Assignment of treatment

- It is a non-comparative, open-label study. All patients will receive the same treatment.

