10.3.2.2 Analysis for secondary variables

For the analysis of these variables, the same primary analysis will be carried out as long as they have the necessary measurements to do so.

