10.3.3 Exploratory Analysis

The analysis of exploratory variables will be carried out in those subjects who conclude their participation without deviations from the study protocol (population by protocol, PP). The same primary analysis will be carried out if they have the necessary measurements to do so.

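### Changes from baseline in a one-arm study are assigned only Kolmogorov-Smirnov (no reference distribution) and Mann-Whitney U (no groups); no paired test is named

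*Combined protocol and SAP*

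**What the plan says.** The study has a single arm; section 7.3 states that "All patients will receive the same treatment". Sections 7.4.2 and 7.4.3 define the quantitative secondary and exploratory outcomes as changes: pupil diameter, near acuity, distance acuity, IOP, surface staining, vital signs and OCI.

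The tests for them are named in three places:

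- Synopsis (1.1), as the analysis intended to rule out differences: "The Kolmogorov-Smirnov statistic will be used for a sample and the Mann-Whitney statistic (when applicable").
- Board 1 (7.4.4), against each of these variables: "Kolmogorov-Smirnov or Mann Whitney U", footnoted as applying when applicable.
- Section 10.3.2.1: the "Kolmogorov-Smirnov statistic for the difference in measurements, once the values have been adjusted with respect to their baseline within everyone", followed by "In cases where applicable, the nonparametric Mann-Whitney U test will be used".

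Section 10.3.2.2 extends this to the secondary variables ("the same primary analysis will be carried out as long as they have the necessary measurements to do so") and section 10.3.3 to the exploratory ones, in the per-protocol set ("The same primary analysis will be carried out if they have the necessary measurements to do so"). Normality is assigned separately to Shapiro-Wilk in 10.3.1. Nowhere does the plan say which distribution the differences are compared with, or which two groups Mann-Whitney compares.

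**The concern.** The question for each of these variables is whether values moved from baseline in the same people. That calls for a paired comparison, or equivalently a one-sample test that the changes are centred on zero. Neither named method is specified as one.

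Kolmogorov-Smirnov compares a whole distribution with a reference. Whether it responds to a shift depends on that reference, which is missing. Mann-Whitney assumes two independent groups. The obvious pair of samples in a one-arm study is baseline and follow-up, and these are not independent.

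At stake is the reading of a non-significant p-value. Section 7.4.5.5 says mydriasis is not expected at this concentration, so a modest average shift in pupil size or near vision is what these analyses could add to the adverse-event data. A test that cannot see such a shift could be reported as evidence of no change.

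**Working it through.** **Inputs from the plan.** Two-sided alpha 0.05 (synopsis). Section 10.1.2 gives 24 subjects raised by 20%: 24 × 1.20 = 28.8, rounded up to 29, which reproduces the stated figure. Results are for n = 29, with n = 24 as the case where the allowed losses occur. One eye per subject (7.4.5).

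**Assumptions.** The documents give no SD, effect size or baseline/follow-up correlation for these variables. I take normal data with equal SD at both visits, correlation ρ from 0 to 0.9, and mean shifts of 0.3, 0.5 and 0.8 baseline SD.

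**1. Kolmogorov-Smirnov against a normal fitted to the same changes.** The test uses z = (change − sample mean) / sample SD. Adding a constant to every change leaves every z the same, so the statistic cannot respond to a mean shift of any size. In simulation it rejected in about 0% of runs at every shift tried. With the Lilliefors correction it rejected in 4–5% of runs, whether the shift was 0, 0.5 or 3 SD.

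**2. Kolmogorov-Smirnov against a zero-centred normal with known SD.** This does detect a shift (table), but it needs a null SD that the plan does not supply.

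**3. Mann-Whitney on baseline against follow-up.** By analogy with means, the variance of the difference is 2(1 − ρ)/n, but an unpaired test assumes 2/n. The nominal cut-off of 1.96 then acts like 1.96/√(1 − ρ):

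- ρ = 0.3: 1.96/0.837 = 2.34, a two-sided error of about 1.9% (simulated 1.8%).
- ρ = 0.5: 1.96/0.707 = 2.77, about 0.6% (simulated 0.8%).
- ρ = 0.8: 1.96/0.447 = 4.38, essentially zero (simulated 0.0%).

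**4. Paired benchmark.** SD of change = √(2 − 2ρ) baseline SDs. At ρ = 0.8 this is √0.4 = 0.632. For a 0.3 SD shift and n = 29 the noncentrality is (0.3/0.632) × √29 = 2.55, and the exact paired t power is 69.4%. The simulated signed-rank power of 67.4% sits just below it, as expected.

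**Rejection rates (%), n = 29.** MW = Mann-Whitney, baseline against follow-up; SR = signed-rank on change; KS0 = Kolmogorov-Smirnov against a zero-centred normal with known SD. Rows ρ = 0 and 0.3 use 4,000 runs, the others 10,000; a dash means not tabulated.

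| ρ | MW, no shift | 0.3 SD: MW | SR | KS0 | 0.5 SD: MW | SR | KS0 |
|---|---|---|---|---|---|---|---|
| 0 | 4.6 | 19 | 19 | – | 45 | 44 | – |
| 0.3 | 1.8 | 16 | 26 | – | 42 | 57 | – |
| 0.5 | 0.8 | 11.9 | 32.6 | 28.7 | 42.2 | 71.2 | 63.9 |
| 0.7 | 0.0 | 7.8 | 50.6 | 44.2 | 42.3 | 90.2 | 85.3 |
| 0.8 | 0.0 | 5.5 | 67.4 | 60.3 | 41.5 | 97.8 | 95.8 |
| 0.9 | 0.0 | 2.5 | 92.0 | 87.2 | 43.2 | 100 | 100 |

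At n = 24 and ρ = 0.5, MW against SR is 9.3% against 28.0% for 0.3 SD, and 34.0% against 63.1% for 0.5 SD. At n = 29 and 0.8 SD, Mann-Whitney still detects 87–97% (ρ from 0.3 to 0.8).

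**The case against.** The strongest defence is that section 10.3.2.1 applies Kolmogorov-Smirnov to within-subject differences, so the pairing is kept, and that Shapiro-Wilk already covers normality, so the fitted-normal reading would make Kolmogorov-Smirnov redundant. That is fair. On the favourable zero-centred reading the loss is only about 2 to 7 points in the table, apart from the ρ = 0.9, 0.5 SD case where both tests reach 100%. But the plan does not state that reading, and it requires a known SD.

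Second, the large Mann-Whitney losses assume it is run across visits. The plan limits it to applicable cases, says in 10.3 that test assumptions will be followed, and uses one eye per subject to protect independence. Board 4 may also place a bivariate code for pupil diameter under photophobia, which would give two genuine groups, although that table's columns may have shifted in extraction. These points make the cross-visit use a risk, not a certainty. They do not supply a test of change from baseline.

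Third, normal data do not represent every variable. For an assumed floor-heavy staining score (about 79% zero at baseline, ρ = 0.8, 0.3 SD latent shift), power is 25% for signed-rank against 4% for Mann-Whitney. The gap persists, but the 67% figure does not carry over.

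Finally, eight measures at two visits plus OCI make 17 tests. If independent, the chance of at least one false positive is 1 − 0.95^17 = 58%. That stands, and the replacement text should address it.

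**Conclusion.** The concern holds. For every quantitative change variable, the plan names one test whose hypothesis is undefined and another whose groups are undefined. Depending on how the gap is filled, power for the same 0.3 SD shift at n = 29 and ρ = 0.8 is near zero, 5.5%, or 60%, against 67% for a standard paired test. The Mann-Whitney loss shrinks as correlation falls and vanishes at ρ = 0. All effect sizes and correlations are assumptions.

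This should be fixed but is not fatal. The outcomes concerned are secondary and exploratory, and the sample size does not rest on them. The two primary outcomes are incidences, outside this point; the Mann-Whitney entry Board 1 also gives them is a separate matter. Large individual changes are recorded as adverse events whatever test is used: pupil change above 2 mm, loss of two or more lines, IOP of 24 mmHg or more, staining of 3 or more. Mean, SD, minimum and maximum are reported regardless. What may be missed is a small to moderate average shift.

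**What to change.** In the synopsis, Board 1 and sections 10.3.2.1 to 10.3.3, replace the Kolmogorov-Smirnov/Mann-Whitney wording for these variables as follows:

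- One Wilcoxon signed-rank test on change from baseline at each visit where the variable is measured: days 7 and 16, and day 16 only for OCI.
- The Hodges-Lehmann estimate of median change with its 95% CI. In a safety study the interval matters more than the p-value, because it shows how large a change remains compatible with the data.
- A stated rule for zero changes, which will be common for staining and for acuity read in lines.
- A sentence saying whether p-values are adjusted for multiplicity or are descriptive.
- Mann-Whitney only where two independent subgroups are named.

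Shapiro-Wilk may stay as description but should not select the test. The cost is wording in the plan; data, visits and sample size are unchanged.
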